### Summary tables

The number (and percentage) of participants with TEAE will be summarized by treatment group and presented by the SOCs in alphabetical order and the PTs in descending incidence in the total column. A patient with multiple AEs within a given category is only counted once for summary purposes. TEAEs, regardless of study drug relationship, will be summarized in the following ways:

- By treatment and PT
- By treatment and SOC
- By treatment, SOC and PT
- By treatment, SOC, PT and maximum severity

Separate summaries by SOC and PT will be provided for:

- TEAEs suspected to be study medication related
- TEAEs leading to treatment discontinuation
- TEAEs leading to dose interruptions and/or adjustments
- Serious treatment emergent AEs

### Listings

Listing will be provided for all AEs and SAEs.

#### 2.7.1.1 Adverse events of special interest / grouping of AEs

The Compound Case Retrieval Strategy (CRS) will be used to determine the MedDRA search criteria to be used to identify events of special interest. The most recent list of adverse events of special interest at the time of database lock will be used.

### Summary tables

- The number (and percentage) of participants who reported treatment emergent adverse events of special interest will be summarized by risk name, PT, maximum severity and treatment group.

In the summary table, risk names will be sorted alphabetically and, within each risk name, the PTs will be sorted in descending order of frequency in the total column. If a patient reported more than one adverse event with the same PT, the AE will be counted only once. If a patient reported more than one AE within the same risk, the patient will be counted only once at that risk.

- SAEs of special interest will also be summarized by risk name, PT, maximum severity and treatment group.

## **2.7.2 Deaths**

### **Summary tables**

Deaths regardless of relationship to study drug by SOC and PT will be summarized on the SAF.

### **Listings**

Deaths will be listed by treatment including the start date of the study treatment, the last date on study treatment, the death date and the primary cause (and contributing cause if any) for death.

## **2.7.3 Laboratory data**

Only central lab parameters will be included in reporting. The summary of laboratory evaluations will be presented for six groups of laboratory tests: Chemistry, Hematology, Urinalysis, Coagulation, Pregnancy Test and additional tests. On presenting abnormalities laboratory data will be grouped and displayed in an alphabetical order within each of the six groups.

### **Summary tables**

- Absolute values and change from baseline will be summarized for continuous laboratory parameters by visit.
- For selected laboratory tests, the number and percentage of participants with newly occurring or worsening laboratory/liver enzyme abnormalities meeting the clinically notable criteria at any time post baseline will be summarized. Clinically notable criteria are defined in [Appendix 5.5](#).

For a participant to meet the criterion of a newly occurring clinically notable value, the participant needs to have a baseline value that is not clinically notable for that parameter. For a participant to meet the criterion of a worsening clinically notable value, the participant needs to have a baseline value that is clinically notable and also have a worse post-baseline value. For participants with missing baseline value, any post-baseline notable value will be considered as newly occurring.

For each participant, all applicable post-baseline values (including unscheduled or unplanned visits) will be checked against the respective criteria. If at least one of the results, for a particular parameter, exceeds the criteria, the participant will be considered as clinically notable abnormal for that parameter. A participant can be counted in both low and high categories. If multiple

abnormality occurrences exist for the same lab parameter, the worst case within a lab parameter will be used to categorize the abnormality.

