As per the USM, participants were to continue with their original VES up to and including Week 29. A new VES was created for Weeks 33, 53 and 69 (see [Table 8-5](#)).

The assessment schedule ([Table 8-2](#), [Table 8-3](#) and [Table 8-4](#)) lists all of the assessments and when they are performed. All data obtained from these assessments must be supported in the participant's source documentation, as appropriate.

Participants should be seen for all visits/assessments as outlined in the assessment schedule or as close to the designated day/time as possible. Refer to [Table 8-1](#) for allowable visit windows. Missed or rescheduled visits should not lead to automatic discontinuation.

If the end of the Blinded Extension has not been triggered by the time participants reach week 53 (i.e., because the results of the DRF are not available), the BE will continue beyond week 53. Participants beyond Week 53 will remain on the assigned dose until the End of Blinded Extension is triggered. Refer to [Table 8-3](#).

The Baseline visit in the OLE is equivalent to the End of Treatment (EOT)-Blinded Extension visit for participants who are still ongoing at the time the End of the BE is declared. Investigators will be notified ahead of time in preparation for transition to OLE. Since the duration of the BE may be different for individual participants, and in order to minimize participant burden, guidance will be provided to Investigators to clarify what BE assessments may be deferred at the final regular BE visit to ensure that they are performed only once as part of the OLE baseline visit, such as LP and MRI.

If the COVID-19 or similar pandemic limits or prevents on-site study visits, alternative methods of providing continuing care may be implemented. Phone calls, virtual contacts (e.g. teleconsult) or visits by site staff/home nursing service to the participant's home depending on local regulations and capabilities, may replace on-site study visits, for the duration of the pandemic until it is safe for the participant to visit the site again. If the Investigator delegates tasks to an off-site healthcare professional, the Investigator must ensure the individual(s) is/are qualified and appropriately trained to perform assigned duties. The Investigator must oversee their conduct and remain responsible for the evaluation of the data collected.

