Neurological Examination	X	X	X	
Vital signs (including body weight)	X	X	X	
Electrocardiogram (ECG)	X			
Hematology	X	X ¹	X ¹	
Clinical Chemistry	X	X ¹	X ¹	
Thyroid Function	X	X ¹	X ¹	
NTproBNP, Troponin	X	X ¹	X ¹	
Pregnancy Test - Serum	X	X	X	
Urinalysis	X	X ¹	X ¹	
Columbia- Suicide Severity Rating Scale (C-SSRS)	X	X	X	
Serum Biomarkers (NfL)	X	X	X	
Nerve Conduction Studies (tibial CMAP/sural nerve SNAP) ²	X	X	X	
Brain MRI	X	X	X	
UHDRS – TFC, TMS, IS, █	X		X	
Adverse Events	X	X	X	
Serious Adverse Events	X	X	X	
Prior and concomitant medications or therapies	X	X	X	
End of Study Disposition				X

Period	Revised follow-up assessment schedule ³			
Visit Name	Wk 33	Wk 53	Week 69	EOS
Days	225	365	477	477
Weeks	33	53	69	69

¹ To minimize burden to participants, it is recommended that safety labs/urinalysis are performed only if required for Adverse Events or follow up of an AE.

² NCS must be performed in triplicate and recommended bilaterally. However, if performed unilaterally, then it should be conducted on the same side as per the screening visit

³ Visit window for Week 33 onwards is ± 2 weeks.

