8.4 Safety/Tolerability

To minimize burden to participants, it is recommended that safety labs/urinalysis are performed only if required for Adverse Events or follow up of an AE. See VES [Table 8-5](#) for list of safety assessments to be performed following the USM.

Safety assessments are specified below with the assessment schedule detailing when each assessment is to be performed.

For details on AE/SAE collection and reporting, refer to [Section 10](#).

Table 8-6 Assessments & Specifications

Assessment	Specification
Physical examination	
A complete physical examination including the examination of general appearance, skin, neck (including thyroid), eyes, ears, nose, throat, lungs, heart, abdomen, back, lymph nodes, extremities, vascular, and neurological will be performed at Screening and Baseline visits. If indicated based on medical history and/or symptoms, rectal, external genitalia, breast, and pelvic exams will be performed.
 
A short physical exam will include vital signs (temperature, blood pressure [SBP and DBP] and pulse) examination of general appearance, head, eyes, ears, nose, throat, neck, skin, lungs, heart and abdomen. Evidence of possible bleeding tendency such as bruises or petechial rash should be noted.
 
Information for all physical examinations must be included in the source documentation at the study site. Clinically relevant findings that are present prior to signing informed consent must be recorded on the appropriate eCRF that captures medical history. Significant findings made after signing informed consent which meet the definition of an Adverse Event must be recorded as an adverse event.

Vital signs	Vital signs include temperature (method of body temperature (i.e. oral) is up to site local practices), BP and pulse measurements. After the participant has been supine for ten minutes, systolic and diastolic blood pressure will be measured three times using an automated validated device, e.g. OMRON, with an appropriately sized cuff. The repeat measurements will be made at 1 - 2 minute intervals. In case the cuff sizes available are not large enough for the participant's arm circumference, a sphygmomanometer with an appropriately sized cuff may be used.
Height and weight	Height and body weight (in indoor clothing, but without shoes) will be measured

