## Figures

- Box-plots for lab parameters will be provided over time by treatment group.

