**Table 5-2      Visit windows for Neurological Exams, nerve conduction studies, weight, urinalysis, C-SSRS**

Label	Start day	Target day	End day
Baseline	See baseline assessment of the Study ( Section 2.1.1 , baseline definition)		
Wk 1			
Wk 2	2	8	11
Wk 3	12	15	22
Wk 5	23	29	43
Wk 9	44	57	71
Wk 13	72	85	99
Wk 17	100	113	127
Wk 21	128	141	155
Wk 25	156	169	183
Wk 29	184	197	211
Wk 33	212	225	239
Wk 37	240	253	267
Wk 41	268	281	295
Wk 45	296	309	323
Wk 49	324	337	351
Wk 53	352	365	421
Wk 69	422	477	until end of study

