**Table 5-3      Visit window for vital Signs, ECG, Hematology, chemistry, NTproBNP, Troponin**

Same as [Table 5-2](#) except the beginning phase:

Label	Start day	Target day	End day
Baseline	See baseline assessment of the Study ( Section 2.1.1 , baseline definition)		
Wk 1	1 (planned post-dose)	1	4
Wk 2	5	8	11
Wk 3	12	15	22
....			

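### By-visit lab means and box plots at Weeks 53 and 69 would rest on samples that the protocol recommends drawing only for an adverse event

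*SAP*

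**What the plan says.** **Sampling.** Protocol Section 8 says of the follow-up after the urgent safety measure: "A new VES was created for Weeks 33, 53 and 69". In that schedule (Table 8-5) the hematology row reads "Hematology X X ¹ X ¹", so it is unconditional at Week 33 and carries footnote 1 at Weeks 53 and 69. Chemistry, thyroid function and NTproBNP/troponin follow the same pattern. Footnote 1 says "it is recommended that safety labs/urinalysis are performed only if required for Adverse Events or follow up of an AE", to spare participants burden. Section 8.4 repeats the advice and points to Table 8-5.

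**Analysis.** SAP 2.7.3 plans: "Absolute values and change from baseline will be summarized for continuous laboratory parameters by visit". Under Figures it adds: "Box-plots for lab parameters will be provided over time by treatment group". The windows come from SAP 5.4. Table 5-3 is titled "Visit window for vital Signs, ECG, Hematology, chemistry, NTproBNP, Troponin" and adopts the Table 5-2 windows after the first weeks. Those include Week 53 (Days 352 to 421) and Week 69 (Day 422 "until end of study"). SAP 5.4 also lets unscheduled samples into the windows and, where values compete, keeps the worst one for safety parameters.

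Nothing in either document stops these outputs at the last routine lab, marks the conditional samples, or asks for the number tested out of the number attending.

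**The concern.** Whether a participant has a lab value at Week 53 or 69 depends, by recommendation, on whether that participant has an AE that calls for one. The by-visit tables and box plots set such values beside Week 33, when labs are due for everyone still attending. A reader would naturally take the sequence from Week 33 to 53 to 69 as the arm's course off drug, although its members change between the first point and the next two.

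The placebo column is unlikely to help. Amendment 02 lets placebo participants leave at Week 33, or at once if they have passed it, so few or no late placebo values are expected.

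Safety is a primary objective still to be reported, and the SAP now plans no modelling. The descriptive table is therefore the result, with no later analysis to correct it.

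**Working it through.** The plan gives no figure to reproduce. The check has four steps.

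**1. Does the revised schedule govern these visits?** The SAP history dates its first version 30-Nov-2021, before the first participant's first visit. Table 8-2 ends screening at Day −7, so Day 1 is at the earliest 30-Nov-2021 + 7 days = 07-Dec-2021. Day 365 is then at the earliest 07-Dec-2021 + 364 days = 06-Dec-2022, the date of the follow-up notice. Essentially all Week 53 visits and all Week 69 visits fall under Table 8-5.

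**2. Sampling rule and output rule side by side**

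| Visit | Sampling (Table 8-5) | Output (SAP 2.7.3, 5.4) |
|---|---|---|
| Week 33 | Routine | By-visit row, box plot |
| Week 53 | Recommended only for an AE or its follow-up | By-visit row, box plot |
| Week 69 | Recommended only for an AE or its follow-up | By-visit row, box plot |

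For hematology, chemistry and NTproBNP/troponin the late windows are explicit. For thyroid no visible window table names the test (parts are blacked out), so only the unrestricted wording of 2.7.3 applies.

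**3. Possible size.** All three inputs are assumptions: q, the share of the arm tested because of an AE; d, the mean shift of that group; r, the chance that anyone else is tested anyway. The others are taken as unshifted.

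- Arm mean = q·d
- Row mean = d·q / [q + (1 − q)·r]
- Bias = row mean − arm mean; with r = 0 this is d − q·d = d(1 − q)

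The planned arm of 25 at 4:1 gives 25 × 4/5 = 20 on branaplam; actual enrolment is not stated. With r = 0:

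| q | Tested of 20 | Bias, d = 1 SD | Bias, d = 0.5 SD |
|---|---|---|---|
| 20% | 4 | 0.80 SD | 0.40 SD |
| 40% | 8 | 0.60 SD | 0.30 SD |
| 60% | 12 | 0.40 SD | 0.20 SD |

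With d = 1 SD and some routine testing despite the advice:

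| q | r = 0.25 | r = 0.5 | r = 1 |
|---|---|---|---|
| 20% | 0.30 SD | 0.13 SD | 0 |
| 40% | 0.33 SD | 0.17 SD | 0 |

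Example: q = 20%, r = 0.25 gives a row mean of 0.2/(0.2 + 0.8 × 0.25) = 0.50 SD against an arm mean of 0.20 SD, a bias of 0.30 SD.

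**4. The worst-value rule.** AE follow-up tends to produce repeat samples. Keeping the worst of two independent, normally distributed values moves the retained value by 1/√π = 0.56 within-person SD on average; the worst of three moves it by 3/(2√π) = 0.85. This applies only to participants with repeats in one window, and it adds to any bias from step 3.

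**The case against.** The strongest reply is that the footnote is advice. The labs stay marked at both visits, and how many participants without an AE were sampled is unknown; if everyone was, the bias is nil. This stands and limits what can be said about size. It does not settle what the rows represent, because the plan does not collect or show the information needed to tell.

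A second reply is that the AEs behind this follow-up are mainly neuropathic (Amendment 02; SAP Table 2-3), and nothing in the documents ties them to shifted hematology or chemistry. This also stands. A reader might infer that the late rows describe sick participants and will show a late deterioration. The documents support only selection by AE: an AE may be mild or unrelated to the parameter, so a shift is possible and not predicted. A reader might also express the distortion as the ratio 1/q, which is 5-fold at q = 20%. That ratio is the same for a trivial and a large d, so the absolute bias is the usable quantity.

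Third, some AE-prompted values never reach these rows, because Protocol 8.4.1 allows local tests and SAP 2.7.3 reports only central ones. That thins the rows without removing the selection.

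Fourth, Week 33 is not a clean cut-off for everyone. The 05-Aug-2022 notice kept monthly visits with scheduled safety labs, and the 06-Dec-2022 notice provides for participants already past Week 33. Some may have routine labs in the Week 37 to 49 windows. This stands and shapes the fix.

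Finally, the analysis is descriptive, and the assessments for which follow-up was extended (neurological examination, nerve conduction, MRI) carry no such condition. That lowers the stakes. The planned listings do not repair the gap: the lab listing covers only participants with a notable value, and flagging unscheduled visits would not mark a conditional sample taken at a scheduled visit.

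**Conclusion.** The point holds for continuous hematology, chemistry and NTproBNP/troponin values at Weeks 53 and 69, and for thyroid so far as 2.7.3 would tabulate it. Followed as written, the protocol makes late sampling depend on an AE, and the SAP summarises the result as if it described the arm. The late rows could show a shift from Week 33 that reflects who was tested.

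The size cannot be estimated from the documents. The range of 0.20 to 0.80 SD with full adherence, falling to zero with full testing, rests on assumed q, d and r, and on untested participants being unshifted. It is zero whenever d is zero.

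Urinalysis is outside the point. The dipstick is local and a sample goes to the central laboratory only after an out-of-range result, so central urinalysis is triggered by findings at every visit. The table of newly occurring or worsening notable values is not misbuilt either: it is meant to count any post-baseline result, though the chance of detection is uneven after routine testing ends.

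**What to change.** In SAP 2.7.3:

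- Limit by-visit lab means and box plots to samples drawn under a routine schedule. That means through Week 33, plus any Week 37 to 49 labs drawn under the original schedule before the 06-Dec-2022 notice.
- Put Week 53 and 69 labs in a separate listing labelled as conditionally sampled, with number tested out of number attending at each visit and the reason for sampling where recorded.
- Keep the notable-value table as planned, with a footnote that ascertainment after the last routine lab visit was conditional.
- Record the change in SAP Section 4, which at present only refers the reader back.

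The cost is SAP wording, one filter on visit and schedule, and one listing. No value is lost, since late results move from summary rows to a listing. The sampling advice itself is untouched.

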## Figures

- Box-plots for lab parameters will be provided over time by treatment group.

## Listings

- Laboratory data of participants with at least one clinically notable value will be listed.

### 2.7.4 Other safety data

#### 2.7.4.1 ECG and cardiac imaging data

##### ECG

TriPLICATE ECGs (3 ECGs are collected) are performed at week 1 and week 9. Regular ECGs are performed for the rest of scheduled visits. ECG clinically significant abnormalities will be recorded on the eCRF as either medical history/current medical conditions or AEs as appropriate. For the analysis of continuous ECG parameter, for triplicate ECG, the mean value of the 3 ECG measurements will be used, for ECG interpretation, all findings of the 3 ECGs will be considered. ECG parameters include heart rate, PR duration, QT duration, QRS duration, QTcF (QT corrected using Fridericia's correction formula).

##### Summary tables

- Absolute values and change from baseline will be summarized for ECG parameters by visit and time point.
- The number and percentage of participants with newly occurring or worsening ECG abnormalities at any post-baseline visits will be summarized.

For derivation of notable values of triplicate ECG, the mean of the triplicate ECGs will be used. Notable criteria are defined in [Appendix 5.5](#).

##### Listings

ECG data of participants with at least one abnormal value will be listed.

#### Echocardiogram with Global Longitudinal Strain (GLS)

Two dimensional echocardiography measurements will be assessed during the study. Central assessment results will be used for reporting.

##### Summary tables

Descriptive statistics will be summarized for the following parameters by visit:

- Left ventricular ejection fraction (LVEF)
- Left Ventricular Global Longitudinal Strain (LVGLS)

The number and percentage of participants with clinically notable values at any post baseline visits will be summarized by period, parameters. The clinically notable are defined in [Appendix 5.5](#).

##### Listings

---

Echocardiogram data will be listed for the participants with clinically notable values.

#### **2.7.4.2 Vital signs**

Vital signs includes temperature, blood pressure (sitting systolic and diastolic) and pulse.

##### **Summary tables**

- Absolute values and change from baseline will be summarized for vital signs parameters by visit.
- The number and percentage of participants with newly occurring or worsening clinically notable vital sign values at any time post baseline will be summarized. Clinically notable changes are defined in [Appendix 5.5](#). All applicable post-baseline values (including unscheduled or unplanned visits) will be checked against the respective criteria.

##### **Figures**

- Box-plots for vital signs parameters will be provided over time by treatment group.

##### **Listings**

- Vital signs data of participants with at least one clinically notable value will be listed.

#### **2.7.4.3 Columbia Suicide Severity Rating Scale (C-SSRS)**

The Columbia-Suicide Severity Rating Scale (C-SSRS) is a questionnaire that prospectively assesses suicidal ideation and suicidal behavior. The C-SSRS must be administered at each visit, including unplanned visits. At the first study visit, the “baseline/screening” version of the C-SSRS will be administered. This version assesses suicidal ideation and suicidal behavior during the participant's lifetime and during a predefined period. At subsequent visits, the “since last visit” version will be administered. AE and SAE will be reported respectively for events of “Non-Suicidal Self-Injurious Behavior” and life-threatening events.

##### **Summary tables**

- Summary showing numbers and percentages of participants who have an answer “yes” to a suicidal behavior or ideation category at any post-baseline visit.
- The number and percentage of participants who have an answer “yes” to a suicidal behavior or ideation category for the lifetime assessment at screening will be included.

##### **Listings**

- All data of participants with any “Yes” on item 4 or item 5 of the Suicidal Ideation section of the CSSRS or any “Yes” on any item on the suicidal behavior section will be listed.

#### **2.7.4.4 Neurological Exam**

Neurological examinations are conducted at each visit to monitor for any clinically significant abnormalities. The exam has three subcategories: Motor function, Deep tendon reflexes and Sensory system. Each subcategory includes multiple exams on various body locations. AE and SAE will be reported respectively in case of clinically significant findings.

A worsening at post BL is defined as: a decrease from baseline and the score is **NOT** normal. In order to systematically summarize the worsening from baseline, the following flags will be created to capture different degrees of worsening and recovery:

Flags by visit and by parameter level:

- By visit flag 1 (worsening): reduced grade (decrease) in at least 2 consecutive visits post BL (same worsening at the same parameter/location/laterality). Flag the last visits with worsening.
- By visit flag 2 (recovery): For participants who met the criterion for 2 consecutive visits, flag visits after **last** visit with worsening (this worsening stands for any worsening and don't have to be consecutive) that the grade is back to baseline

Flags by participant level and by three **subcategories** based on the above visit-based:

- participant level flag 1: Participant without any worsening at 2 consecutive visits by Motor function, DTR, and Sensory
- participant level flag 1.5: Participant without any worsening at 2 consecutive visits in any subcategory
- participant level flag 2 (worsening): Participant with any worsening at 2 consecutive visits by Motor function, DTR and Sensory
- participant level flag 3 (recovery): Participant with any worsening at 2 consecutive visits followed by recovery (worsening no longer present in all parameters within the category) by Motor function, DTR and Sensory
- participant level flag 4 (partial recovery): Participant with any worsening at 2 consecutive visits followed by partial recovery (worsening no longer present in at least one of the parameters within the category) by Motor function, DTR and Sensory
- participant level flag 5 (overall worsening): Participant with worsening at 2 consecutive visits in any subcategory
- participant level flag 6 (overall recovery): Participant with worsening at 2 consecutive visits in any subcategory followed by recovery (recovered in all parameters)
- participant level flag 7 (overall partial recovery): Participant with worsening at 2 consecutive visits in any subcategory followed by partial recovery (worsening no longer present in at least one of the parameters)

Note that flags will be created based on weekly basis window instead of protocol scheduled visit window.

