**Table 2-4 Example of consecutive worsening and recovery for Neuro Exam**

Visit	Scenario 1 No consecutive worsening	Scenario 2 consecutive worsening followed by recovery	Scenario 3 consecutive worsening NOT followed by recovery
Baseline	normal	normal	normal
Wk1	normal	normal	normal
Wk2	decrease	decrease	normal
Wk3	normal	decrease	decrease
Wk5	decrease	normal	decrease
Wk9	normal	decrease	normal
Wk13	decrease	normal	decrease
...			

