#### 2.7.4.5 Neuropathy questionnaire

For neuropathy symptoms: worsening is defined for participants with a change in answer from “No” at baseline to “Yes” at post BL.

Flags by visit and by parameter level:

- By visit flag 1: adverse change indicated by a “YES” response to the same question in the questionnaire in at least 2 consecutive visits. flag the last visit with finding
- By visit flag 2: adverse change indicated by a “YES” response to a question in the questionnaire at any post baseline visit
- By visit flag 3 (recovery): Flag visits after **last** visit with finding (this finding stands for any worsening and don’t have to be consecutive) that the answer is back to baseline

Flags by participant level based on the above visit-based:

- Participant level flag 1: Participant without any finding at 2 consecutive visits
- Participant level flag 2: participants with any finding at 2 consecutive visits

- Participant level flag 3 (recovery): participants with any finding at 2 consecutive visits and followed by recovery (finding no longer present in all worsened questionnaire)
- Participant level flag 4 (partial recovery): participants with any finding at 2 consecutive visits and followed by partial recovery (finding no longer present in at least one of the worsened questionnaire)
- Participant level flag 4: Participant without any finding at any visit
- Participant level flag 5: participants with any finding at any visit
- Participant level flag 6 (recovery): participants with any finding and followed by recovery (finding no longer present in all worsened questionnaire)

Participant level flag 6.5 (partial recovery): participants with any finding and followed by partial recovery (finding no longer present in at least one of the worsened questionnaire) Note that, flags will be created based on weekly basis window instead of protocol scheduled visit window.

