#### 2.7.4.7 Overall safety findings and recovery

Results from Neuro findings including: NCS, neuro exam, symptoms (AEs and neuro questionnaire) will be summarized in one table for participants on active to show number (%) of participants with finding together with the information about recovery (yes/no) at the end of observation.

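### Neurological worsening must be seen at two consecutive visits but recovery at only one, so the final examination alone can decide the recovery label; show confirmed and single-visit recovery separately

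*SAP*

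**What the plan says.** SAP 2.7.4.4 sets by-visit flag 1 (worsening) as "reduced grade (decrease) in at least 2 consecutive visits post BL", in the same parameter, location and side. By-visit flag 2 (recovery) reads "For participants who met the criterion for 2 consecutive visits, flag visits after" the last worsened visit "that the grade is back to baseline". It sets no minimum number of such visits. It also says that "this worsening stands for any worsening", so a single later abnormal reading resets recovery.

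At participant level, full recovery needs every parameter in the subcategory to have cleared. Partial recovery needs only one.

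Table 2-4 gives worked examples. Scenario 2, headed "consecutive worsening followed by recovery", runs: normal at Week 1, decrease at Weeks 2 and 3, normal at Week 5, decrease at Week 9, normal at Week 13, with the table left open after that.

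SAP 2.7.4.5 builds the questionnaire flags in the same way; its recovery flag ends "have to be consecutive) that the answer is back to baseline". It also defines a second set of flags for any finding at any visit, with their own recovery.

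SAP 2.7.4.7 carries the results into one active-arm table giving "information about recovery (yes/no) at the end of observation".

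**The concern.** The two-visit rule for worsening guards against acting on one unreliable examination. Nothing guards the recovery side, and the SAP gives no reason for treating an isolated normal result differently from an isolated abnormal one.

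This matters because assessing signs and symptoms of peripheral neuropathy is a stated purpose of keeping branaplam participants in follow-up (Protocol, Amendment 02 rationale), and recovery is tabulated as a yes/no result. Late examinations are few. Protocol Table 8-5 schedules Weeks 33, 53 and 69 (days 225, 365 and 477), so the last two are 477 - 365 = 112 days, or 16 weeks, apart. A participant still worsened at Week 53 has one scheduled examination left, and it fixes the label. Sites were unblinded on 07-Dec-2022 (Protocol 6.4), so examinations after that date are read with treatment known.

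**Working it through.** **Reproducing the SAP's own example.** I applied the two by-visit flags as written to Table 2-4, post-baseline visits in order (n = normal, d = decrease).

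| Scenario | Wk 1, 2, 3, 5, 9, 13 | Two consecutive d? | Normal visits after last d | SAP rule | If two normal visits were needed |
|---|---|---|---|---|---|
| 1 | n d n d n d | No | 0 | No consecutive worsening | Same |
| 2 | n d d n d n | Yes | 1 | Recovery | Not confirmed |
| 3 | n n d d n d | Yes | 0 | Not recovered | Same |

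All three SAP labels reproduce. Scenario 2 shows that one normal visit is enough, even though an earlier normal visit (Week 5) was followed by a new decrease. Scenarios 2 and 3 each have three abnormal visits out of six; the last visit separates them.

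**Size for one parameter.** Let p be the chance that a truly persistent deficit is recorded as back to baseline at a visit. The documents give no value, so p = 5-30% is an assumption, as is independence between visits. Under the SAP rule, false recovery occurs when the last visit is misread: probability p. If the last two visits must both be at baseline, it is p².

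**Size with two affected parameters,** errors independent between them: false full recovery under the SAP rule is p × p = p²; false partial-or-better recovery is 1 - (1 - p)².

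| p | One parameter, SAP rule | One parameter, two visits | Two parameters, full, SAP rule | Two parameters, at least one cleared, SAP rule |
|---|---|---|---|---|
| 5% | 5% | 0.25% | 0.25% | 9.8% |
| 10% | 10% | 1% | 1% | 19% |
| 20% | 20% | 4% | 4% | 36% |
| 30% | 30% | 9% | 9% | 51% |

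If errors within one examination are fully correlated, false full recovery stays at p however many parameters are affected.

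**Simulation check.** I simulated one parameter with persistent loss from Week 13 and examinations at Weeks 13, 17, 21, 25, 29, 33, 53 and 69 (200,000 runs per p). Among runs meeting the two-visit worsening rule, false recovery was 5.0%, 10.0%, 20.0% and 29.2% under the SAP rule, and 0.25%, 1.0%, 3.9% and 8.4% with two visits. The small shortfall at p = 30% arises because 3.5% of runs never met the worsening rule.

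**Error in the other direction.** Let q be the chance that a truly recovered parameter is read as abnormal. Under the SAP rule it is called not recovered with probability q. If two normal visits were required it would miss recovery with probability 1 - (1 - q)²: 9.75% at q = 5% and 51% at q = 30%. With π the share truly recovered, the net bias of the SAP rule for one parameter is p(1 - π) - qπ. When p = q this is p(1 - 2π): positive below π = 0.5, zero at 0.5, negative above.

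**The case against.** The strongest reply is that the direction of bias is not established. Recovery counts only after the last worsened visit, and any single abnormal reading resets it, so a normal visit in mid-follow-up earns nothing and a false-abnormal final reading hides a true recovery. This stands: a reader might infer that the rule overstates recovery on balance, but the documents give none of p, q or π.

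A reader might also take 5-30% as the share of participants wrongly called recovered. The documents do not support that either. It is a one-parameter figure on an assumed error rate. SAP 2.7.4.4 covers several body locations per subcategory, and full recovery needs all worsened parameters to clear. Partial recovery already has its own row, although it is the more exposed label.

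Nor is Table 2-4 wrong, or evidence that examinations fluctuate. It is an illustration, it follows the stated rule, and it does not show Week 13 to be the final visit.

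Two further points stand in part. The questionnaire tables also report any-visit findings, where one visit suffices on both sides, so the asymmetry there concerns only the two-consecutive-visit flags. And status at the end of observation is a legitimate target that necessarily leans on the last visit; but the table does not tell the reader whether that status rests on one examination or several.

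Finally, replacing the recovery definition would have a real cost: at q = 5-30% a truly recovered parameter would be confirmed at two visits with probability (1 - q)², or 90% to 49%, against 95% to 70% under the SAP rule. That is an argument for adding a row and against redefining recovery.

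**Conclusion.** The asymmetry is real. It is in the text of SAP 2.7.4.4 and the two-consecutive-visit flags of 2.7.4.5, is confirmed by Table 2-4 Scenario 2, and passes into the 2.7.4.7 table. It can overstate recovery: for one persistently abnormal parameter and an assumed per-visit false-normal rate of 5-30%, by 5-30%, against 0.25-9% with two visits, assuming independent errors between visits. Whether it overstates recovery on balance cannot be determined from the documents. The analysis is descriptive, so no test is affected; what is at stake is how a reader interprets a count of recovered participants. A low-cost reporting change resolves it.

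**What to change.** Keep the existing recovery flag. In the tables under SAP 2.7.4.4 and 2.7.4.5 (two-consecutive-visit flags) and in the 2.7.4.7 table, split the participants who carry it into two rows:

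- *Confirmed*: back to baseline at the participant's last two or more consecutive visits, for every parameter that met the two-visit worsening rule.
- *Back to baseline at the last visit only (unconfirmed)*: the remainder.

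Use each participant's own last visits, not fixed Weeks 53 and 69. Placebo participants may leave at Week 33, or immediately if that visit is complete (Protocol Table 8-5 and the text before it), and fixed weeks would not suit the by-group tables. Add a footnote to Table 2-4 that Scenario 2 would be unconfirmed if Week 13 were the last visit.

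The cost is SAP wording and one extra row per table. No new visits or data are needed, and the two rows add up to the existing flag, so nothing is discarded. The drawback is that participants with only one visit after their last worsening, including those who truly recovered late, can only be shown as unconfirmed. The footnote to the table should say so, so that the row is not read as doubtful recovery.
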